## **5.2. Exclusion criteria**

Patients who present any of the following criteria for exclusion cannot be included in the clinical trial:

1. Inability to accept the privacy policy and terms of use of Hyfe.
2. Lack of access to a Wi-Fi network at the site of residence (for objectives 1 and 2).
3. Unwillingness to regularly use the cough-surveillance system throughout the monitoring period.

The investigator shall try to ensure that the participant completes the required monitoring period. The data of the withdrawn patients shall be collected up to the moment of withdrawal. Losses to follow up will not be replaced.

The withdrawal shall be documented in the patient's clinical history and informed to the researchers via a form to be filled online by the patient.

## **6. DESCRIPTION OF THE TOOL STUDIED**

[figure not shown]
Hyfe is an AI-enabled mobile app that records short snippets (<0.5 seconds) of putative cough explosive sounds and then classifies them as cough or non-cough using a convolutional neural network (CNN) model. Briefly, the acoustic characteristics of recorded sounds are converted into an image file, which is then processed by an algorithm trained to identify graphical differences in images. This creates an adjustable prediction score, with values above it, resulting in a sound being classified as “cough”, and those below being classified as “non-cough” (Figure 1).

This allows the discrimination of cough-like sounds from the rest. Cough sounds are then matched with time and GPS coordinates.

The preliminary analytical performance of the system, understood as its sensitivity and specificity differentiating cough episodes from similar recorded sounds, has been validated in an ongoing study in the province of Navarra, Spain (Gabaldon-Figueira et al, 2021). Between November 2020 and January 2021, Hyfe™ registered nearly 700,000 putative cough sounds, from 62 recruited participants. Of these, 119,876 were manually classified by human observers, revealing a sensitivity of 96.34%, and a specificity of 96.54% with a cough-positivity score threshold set at 0.85 (Figure 2). However, since these records exclusively include explosive sounds detected by the application’s algorithm (ignoring coughs that might have

been catalogued as non-explosive sounds, and therefore not furtherly analyzed), this analytical performance must be validated in a real-life scenario, comparing it to continuous records obtained from participants.

Hyfe Air is a wearable device with an incorporated wireless lapel microphone. The device's recordings can be run through the same cough-detection algorithm described above, while its results are directly stored in a remote database and are not displayed to participants. While the algorithm is the same, differences in the characteristics of the incorporated microphone compared to those in smartphones suggest that the device's performance might differ from those previously reported, requiring an independent validation process.

*Figure 1: Audio recordings (bottom) are converted to image files (top) and compared with existing datasets using a CNN. Data not published.*

[figure not shown]

Figure 2: Analytical performance of Hyfe as evaluated in cough records collected between November 2020 and January 2021. Taken from Gabaldon-Figueira et al (2021).

### **6.1. Drugs or treatments that are permitted (including rescue medication) and not permitted before and/or during the trial**

No medications or specific treatments will be prescribed to participants as part of this study. Participants shall continue with any pre-established treatment, or those newly prescribed by their treating doctor during the study period. All treatment prescribed will be recorded in the patients file and study database.

## **7. EVALUATION OF RESPONSE**

### **7.1. Study plan and procedures**

#### **7.1.1. Obtaining consent**

A written informed consent must be obtained before carrying out any of the specific procedures of the study. Part of the process of the informed consent consists of clearly explaining the purposes, methods, objectives, and risks of the study to the patient, their family or legal representative. A copy of the informed consent, also signed by the investigator, shall be kept with the clinical documentation. Another copy shall be given to the patient.

The physician shall record the patient's consent to participate in the study in his/her clinical documentation.

Once consent is obtained, the treating physician will be asked to fill a medical information questionnaire (see attached) which will include information on the patient's demographics, diagnosis and past relevant medical history.

In the case of minors, the informed consent will be signed by parents or legal guardians. All adolescents aged 12-17 will provide informed assent.

### **7.2. Efficacy variables**

For the primary objective 1, efficacy will be measured by determining Hyfe's capacity to predict a diagnosis, or reflect clinical evolution of patients, based on cough signatures. For this, the acoustic characteristics of coughs (mean frequency, volume, amplitude) registered from participants with an etiologic diagnosis, will be described, to identify patterns associated to specific conditions. Additionally, the Area Under the Curve, sensitivity, and specificity of the AI system will be retrospectively evaluated with the annotated cough registries.

For the secondary objective 1, the efficacy variable will be the daily score in the online VAS, and the coughs per recorded hour.

For the secondary objective 2, there is no clear efficacy variable. We will retrospectively include anonymous coughs registered in patients with an etiologic diagnosis and annotated with data in online datasets from where they can be used to train this and similar AI systems in the future.

For the secondary objectives 3 and 4, efficacy variables will include the calculated sensitivity, specificity, positive predictive value (PPV), and negative predictive value (NPV) of Hyfe, compared to two trained human observers.

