### **Assessment of correlation with self-reported questionnaires**

Participants will be asked to complete a daily online, standardized 100mm cough visual analogue scale (VAS), as described by Boulet et al in 2015. Participants will also be instructed to fill a validated Spanish version of the Leicester Cough Questionnaire (LCQ) (Muñoz et al, 2016) at the time of recruitment, and again at the end of the monitoring period.

These records will be compared with those registered by the cough surveillance system. We will evaluate the correlation between the mean weekly VAS score and the registered cough frequency.

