## 9. STATISTICS

### ***9.1. Description of the statistical methods to be used, including the schedule of all the planned intermediate analyses***

For completion of the primary objective

To assess the accuracy of the cough surveillance system to detect cough patterns associated to specific diseases, we will use participants in which an etiologic diagnose is reached before completion of the study. We will search for digital footprints of singular detected cough events, and/or the pattern of cough in time for participants with a given diagnosis.

These records will be used to train a previously developed convolutional neural network to perform respiratory disease cough classification. We will initially use a random split-sample approach (70% derivation & 30% validation) to assess the performance of the newly generated cough classification tool (sensitivity, specificity, positive and negative predictive values, AUC). Performance will then be validated by retrospectively analyzing these participants' coughs with the newly trained AI-network.

The cough classification tool will be supplemented with patient-specific information to assess the incremental value of cough-based multi-variable prediction.

For secondary objective 1

The daily VAS score of participants will be compared to the cough frequency registered by the cough surveillance system. These data will be used to fit a linear regression model to compare self-reported VAS scores to daily cough frequency and calculate a correlation coefficient ( $r$ ). The

average weekly VAS score and cough frequency on week 1, will be compared to that at study withdrawal using a paired t-test, and represented using before-after plots. P values below 0.05 will be considered significant. A similar approach will be used to compare results of the LCQ at the beginning vs the end of the study. Before-after plots will be constructed to represent these differences. This approach is also expected to provide information on the system's capacity to reflect clinical evolution of participants (Primary objective).

For completion of secondary objective 2

Cough registries of participants with an etiologic diagnosis of respiratory disease will be included in annotated datasets. There are no specific statistical analysis required for completion of this objective.

For completion of secondary objectives 3 and 4

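### Clinical evolution is part of the primary efficacy variable, but the protocol text specifies no disease-status reference at follow-up, and the before-after t-tests cannot show that cough tracks it

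*Combined protocol and SAP*

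**What the plan says.** - **Primary variable.** Under section 7.2, primary efficacy is judged by whether Hyfe can either predict the diagnosis or "reflect clinical evolution of patients, based on cough signatures". The measures that follow are acoustic characteristics, which "will be described, to identify patterns associated to specific conditions", and AUC, sensitivity and specificity on the annotated registries. These address diagnosis. No variable is given for evolution.
- **Analysis of evolution.** Section 9.1, under secondary objective 1, plans a linear regression and correlation of VAS on daily cough frequency. It also plans paired t-tests of weekly VAS and cough frequency (week 1 against withdrawal), with a similar approach for the LCQ. It expects this to inform on the system's "capacity to reflect clinical evolution of participants (Primary objective". Section 9.2 likewise sends the sample size for evolution to secondary objective 1.
- **Physician data.** Section 7.1.1: "Once consent is obtained, the treating physician will be asked to fill a medical information questionnaire", "which will include information on the patient's demographics, diagnosis and past relevant medical history". Section 6.1 adds: "All treatment prescribed will be recorded in the patients file and study database". Response to treatment is not mentioned.
- **Repeated data.** The subsection on self-reported questionnaires in section 4.1 has a daily cough VAS, the LCQ "at the time of recruitment, and again at the end of the monitoring period", and a correlation of mean weekly VAS with cough frequency.
- **Comparator.** Section 2.1 names self-perceived improvement as the comparator for treatment response in chronic cough of unknown origin, as one example of use. Section 3 makes the questionnaires the thing assessed against Hyfe.

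**The concern.** To show that cough reflects clinical evolution, the analysis must relate each patient's change in cough to that patient's change in condition. A paired t-test does not. It asks whether the average moved, and it averages patients who improved with those who did not.

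Participants enter because they complain of cough (section 5.1) and there is no control group, so a fall in mean cough over a month is plausible whatever the disease does. Read as section 9.1 is written, such a fall would count as evidence on one limb of the primary objective. The reverse error is also possible: if some patients improve and others worsen, the mean may not move even though cough follows the disease closely.

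The regression does relate two measures to each other, but on levels. Patients who cough more may rate themselves higher throughout, and that alone produces a correlation without either measure moving with the disease.

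**Working it through.** **1. The plan's own figure.** Inputs from section 9.2: effect size 0.35, one predictor, alpha 0.05, power 80%, 10% loss. The index is not named; I read it as Cohen's f². For the F test of R² = 0, the noncentrality is f² × N. The smallest N with power of at least 0.80 is 25 (noncentrality 0.35 × 25 = 8.75, power 0.809). Then 25 / 0.9 = 27.8, rounded up to 28. The stated 28 is reproduced. The implied correlation is √(0.35 / 1.35) = 0.51. The 28 is therefore sized for association between VAS and cough frequency, not between cough change and disease change.

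**2. What the paired t-test responds to.** Assumptions, none from the documents: 25 completers, two-sided alpha 0.05, and a mean fall of 0.6 or 0.8 SD of the change, unrelated to clinical course.

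- 0.6 SD: noncentrality 0.6 × √25 = 3.0, 24 df, power about 0.82.
- 0.8 SD: noncentrality 0.8 × √25 = 4.0, power about 0.97.

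The relation between cough change and clinical course does not enter this formula.

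**3. Simulation of the same point.** 20,000 replicates, n = 25, normal changes, the same standardized mean change in cough and in clinical state, and within-patient correlation 0 or 0.5 between the two changes. Entries are proportions significant.

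| Mean change (SD) | Correlation of changes | Cough t-test | Both t-tests | Change-versus-change correlation |
|---|---|---|---|---|
| 0 | 0 | 0.05 | 0.002 | 0.05 |
| 0 | 0.5 | 0.05 | 0.01 | 0.75 |
| 0.6 | 0 | 0.82 | 0.68 | 0.05 |
| 0.6 | 0.5 | 0.82 | 0.72 | 0.75 |
| 0.8 | 0 | 0.97 | 0.94 | 0.05 |
| 0.8 | 0.5 | 0.97 | 0.94 | 0.75 |
| 1.0 | 0 | 0.998 | 0.996 | 0.05 |
| 1.0 | 0.5 | 0.998 | 0.996 | 0.75 |

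The t-test results are almost the same whether or not cough tracks clinical state. The change-versus-change test separates the two cases. The second row shows the reverse error: real tracking with no mean change, which the t-test does not see.

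**4. Precision of an AUC for improved versus not.** Hanley-McNeil with assumed AUC A = 0.75: Q1 = A / (2 − A) = 0.600, Q2 = 2A² / (1 + A) = 0.643, A² = 0.5625.

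- 15 improved, 10 not: variance = [0.1875 + 14 × 0.0375 + 9 × 0.0804] / 150 = 0.00957, SE 0.098, 95% CI about 0.56 to 0.94.
- 20 improved, 5 not: variance = [0.1875 + 19 × 0.0375 + 4 × 0.0804] / 100 = 0.0122, SE 0.111, 95% CI about 0.53 to 0.97.

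**The case against.** A reader might infer that the study has no follow-up measure, or no reference of any kind, for evolution. The documents do not support that. Section 2.1 names self-perceived improvement for one use, VAS and LCQ are repeated, and section 9.1 includes a regression that tests association. For chronic cough of unknown origin, self-rated cough is arguably part of clinical evolution. This narrows the point but does not remove it. Section 2.2 also covers tuberculosis, NTM and asthma, where a cough rating is not disease status. Section 3 treats the questionnaires as the thing under assessment, so using them alone to validate Hyfe is partly circular. No change-versus-change analysis is specified.

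A reader might also infer that disease course is recorded nowhere. That goes too far. The medical questionnaire is cited as an attachment and cannot be seen here. Case report forms draw on the clinical history (section 12.1). Later diagnoses are captured (section 4.1, annotated datasets), and so are treatments (section 6.1). What can be said is that the protocol text specifies no disease-status reference during follow-up.

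The 0.82 is not an estimate of how often this study would mislead. The size of the fall and its independence from clinical course are both assumed. Nor is the 28 miscalculated.

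Objections to the remedy also stand in part. No end-of-monitoring physician contact is described for outpatients, and a physician's rating may itself lean on what the patient reports about cough.

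**Conclusion.** The concern holds in this form: evolution is a limb of the primary efficacy variable, the text specifies no disease-status reference for it at follow-up, and the before-after t-tests assigned to it cannot show that cough changed in the patients who improved. That insensitivity is structural and does not depend on the assumed effect sizes. The figures (about 0.82 at 0.6 SD and 0.97 at 0.8 SD, with 25 completers) only illustrate it. The planned regression gives partial information: association of levels with self-rated cough. The conclusion relies on section 7.1.1's description of a questionnaire that is not reproduced in the text.

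**What to change.** In section 9.1, state that the before-after t-tests and plots are descriptive and do not support a claim that Hyfe reflects clinical evolution. Define the evolution analysis as within-patient change in coughs per recorded hour against change in a reference:

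- **All participants:** change in VAS and in LCQ, both already collected.
- **Where available:** a treating-physician rating of the disease as improved, unchanged or worse, made without sight of Hyfe counts, at discharge or taken from the next routine contact or the clinical history.

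Report estimates with confidence intervals (for example a change-versus-change correlation, and an AUC for improved versus not), pooling all monitored participants rather than only the 28. Name the reference in section 7.2.

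The cost is SAP wording and one short rating per participant. Some outpatient ratings will be missing, and the physician rating will not be fully independent of reported cough. With about 25 participants the AUC interval would be wide (about 0.56 to 0.94 at an assumed 0.75 with a 15/10 split), so it should be presented as estimation.

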### **2.1. Investigational diagnostic intervention**

We will evaluate the potential role of the mobile app Hyfe Cough Tracker™ as a tool to screen for, diagnose and support clinical management of respiratory diseases. For example, among other potential applications, we will use digital cough monitoring to monitor response to

treatment in patients with a diagnosis of chronic cough of unknown origin, and compare it with self-perceived improvement, while enriching a dataset of disease-specific annotated coughs. Hyfe Cough Tracker™ has been developed by a multidisciplinary team including medical doctors, data scientists and software developers, for mobiles using Android and IOS operative systems. It runs in the background of the mobile, having constant access to the microphone. However, it only records explosive sound snippets of 0.5 seconds or less. These records are then relayed to a remote server, where they are classified by the convolutional network as “coughs” or “not coughs”. Sounds labeled as coughs are then registered both in the app, and in a dashboard accessible by researchers. Hyfe does not record any sound longer than 0.5 seconds, therefore, it will not register conversations or background sound, protecting the privacy of participants. The algorithm can be used on the recordings from a wearable recording system incorporating a lapel mic, which can be used to monitor cough continuously in the absence of a smartphone (Hyfe Air).

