## **4. DESIGN OF TRIAL**

### **4.1. Global design**

This is a single center study to be carried out at the two campuses of the Clínica Universidad de Navarra, in the cities of Pamplona, and Madrid, Spain.

For the cough-monitoring process, we will use, an Artificial-Intelligence system (AI) that detects and records explosive putative cough sounds and identifies human cough based on acoustic characteristics (see below).

Potential participants either attending the outpatient clinic or hospitalized with a complaint of cough will be invited by their treating physician, or a member of the research team and included in the study by part of the research team. A researcher will instruct participants on how to install and use Hyfe Cough Tracker in their smartphones. If necessary, the researcher might provide participants with a smartphone configured to exclusively run Hyfe Cough Tracker™. Researchers who enroll participants will also be responsible of obtaining informed consent forms personally.

Once turned on, the app will monitor cough. Participants provided with a study phone will be instructed to run the app continuously and keep the study smartphone close to them for the period of monitoring.

Depending on the objective, participants will either be submitted to diagnostic procedures deemed necessary by their attending physician or will receive the treatment recommended by their attending physicians and will be monitored for a variable period.

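### Cough volume and amplitude are to be read as disease patterns, but phone, distance and care setting vary between participants and the plan neither records phone and placement nor adjusts for device or setting

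*Combined protocol and SAP*

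**What the plan says.** Section 7.2 of the protocol measures efficacy for the primary objective partly by describing "the acoustic characteristics of coughs (mean frequency, volume, amplitude) registered from participants with an etiologic diagnosis", and gives the purpose as "to identify patterns associated to specific conditions". Section 9.1 then trains a convolutional network to classify coughs by disease and assesses it with a random split, 70% derivation and 30% validation. After that, the same participants' coughs are analysed retrospectively with the trained network.

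The recording conditions for these data are set in several places:

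- **Phone.** Section 4.1 states: "A researcher will instruct participants on how to install and use Hyfe Cough Tracker in their smartphones". Where needed, a study phone dedicated to the app may be supplied instead. Section 2.1 describes the app as built "for mobiles using Android and IOS operative systems". No phone model is required.
- **Distance.** The only placement instruction for the clinical cohort is in section 4.1: "Participants provided with a study phone will be instructed to run the app continuously and keep the study smartphone close to them". It is addressed to study-phone users. No distance is set or measured for anyone.
- **Setting.** Section 5.1 admits inpatients and outpatients. Under Monitoring period, inpatients are followed until discharge and outpatients for an initial month.

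The technical sub-study (Validation of Hyfe's technical performance) does control these conditions: phones of one model, about 50 cm, a quiet room. Those controls apply to cough detection in that sub-study and not to the disease-pattern data.

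**The concern.** Volume and amplitude are properties of the recording as well as of the cough. The same cough gives a different level on a different phone, at a different distance or in a different room. If people with one diagnosis tend to be recorded under one set of conditions and people with another diagnosis under another, a difference in level between the diagnoses can arise with no difference in the coughs.

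This bears on the primary objective. An apparent acoustic pattern, and a classifier that exploits it, could be reported as evidence that cough sound identifies disease. The validation in section 9.1 would not warn of it. Derivation and validation sets are random parts of one cohort, so an association between set-up and diagnosis is present in both. The later retrospective analysis uses the same participants. Collecting more coughs per diagnosis (section 9.2 anticipates 15,500, with 200 time series) makes such a difference more precise without removing it.

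The clips are also meant for annotated datasets on which other systems can be trained. Section 3 names only demographic and medical data as annotation, so later users may be unable to separate disease from set-up.

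**Working it through.** The documents give no figure on this point, so there is nothing to reproduce. The check has three steps.

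**1. Is there a safeguard in the text?** Section 7.2 lists the features and their purpose, with no calibration or normalisation of level. Section 9.1 has no stratification, matching or adjustment by device or setting. The only covariates it adds are patient-specific information, to assess incremental value. Section 7.1.1 describes the medical questionnaire as covering demographics, diagnosis and history. Phone and placement are not mentioned. Section 6 says sounds are converted to an image before classification, but not whether level is normalised at that step.

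**2. How far can level move with distance alone?** Assumptions: free-field spreading, and distances chosen for illustration. Only about 50 cm appears in the documents, and for the sub-study. Level change = 20 × log10(distance ratio).

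- 0.25 m to 0.5 m: 20 × log10(2) = 6 dB lower
- 0.5 m to 1 m: 20 × log10(2) = 6 dB lower
- 0.5 m to 2 m: 20 × log10(4) = 12 dB lower, amplitude one quarter

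This shows how variable level can be. It does not yet show confounding with diagnosis.

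**3. What could an imbalance do?** Take two diseases with no true acoustic difference. Shares s1 and s0 of them are recorded in a set-up that is D dB louder, and the standard deviation of level within a set-up is sd. None of these inputs is in the documents. The AUC of level alone is

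AUC = s1(1−s0)·a + (1−s1)s0·(1−a) + 0.5·[s1·s0 + (1−s1)(1−s0)], with a = Φ(D/(sd·√2)).

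With D = 6 dB and sd = 6 dB, a = Φ(0.707) = 0.760. For shares of 80% and 20%:

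0.64 × 0.760 + 0.04 × 0.240 + 0.5 × (0.16 + 0.16) = 0.486 + 0.010 + 0.160 = 0.656.

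A simulation of this case gave 0.657.

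| Share in louder set-up (disease 1 / disease 2) | AUC of level alone |
|---|---|
| 50% / 50% | 0.50 |
| 60% / 40% | 0.55 |
| 70% / 30% | 0.60 |
| 80% / 20% | 0.66 |
| 90% / 10% | 0.71 |

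For the 80%/20% case, offsets of 3 to 12 dB and standard deviations of 4 to 8 dB give AUCs from 0.56 to 0.79. With balanced set-ups the AUC is 0.50 whatever the offset, so the false signal depends wholly on an association between set-up and diagnosis.

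**The case against.** The strongest reply is that no passage shows this association. Section 9.2 contrasts chronic cough with acute conditions only for how quickly coughs accrue, not for where patients are recorded. A reader might infer that acute disease will be recorded in inpatients and chronic cough in outpatients, in different rooms. That is plausible, but it is inference. Without the association the result is noise, not a false pattern. This part of the reply stands.

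Three other inferences also go too far.

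- **That the plan compares raw levels between diagnoses.** Section 7.2 says only that the characteristics will be described. It does not say raw and names no test. Whether the network can use level at all depends on the image conversion, which is unspecified. Section 9.1 also uses the pattern of cough in time, which does not rest on volume or amplitude.
- **That the protocol concedes the problem for its clinical cohort.** The remark in section 6 on "differences in the characteristics of the incorporated microphone compared to those in smartphones" concerns the Hyfe Air wearable and its cough-detection performance. It supports the general idea that microphones matter. It says nothing about differences between smartphones or about disease patterns.
- **That a disease claim should be allowed only above what device and setting alone predict.** Being an inpatient can reflect severity or type of disease, so such a hurdle could discard true information.

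The medical questionnaire itself is not reproduced in the documents, so a device field cannot be wholly excluded. Setting should be known in any case, since it determines the monitoring period. The omission remains: the text does not say how level is handled, and phone and placement are not among the data it describes.

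**Conclusion.** The point holds in conditional form. Volume and amplitude are to be used to identify disease patterns while phone, distance and setting are free to vary, and the plan contains no stated handling of level and no adjustment for device or setting. If set-up is associated with diagnosis, the description, and possibly the network, can separate diagnoses by recording conditions, and the planned split cannot expose it. If it is not, the cost is added noise.

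The size cannot be derived from the documents. The 12 dB figure rests on assumed distances and free-field conditions, which need not hold in hospital rooms or daily life. The AUCs rest on assumed offsets, standard deviations and shares. They show that a moderate imbalance could matter, not that it will occur. That distance varies is itself inferred from the absence of a fixed distance. The change is worth making because it is cheap and because phone and placement may not be recoverable later.

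**What to change.** In sections 7.2 and 9.1:

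1. Record for each participant the phone model, whether it is the participant's own or a study phone, its usual placement, and inpatient or outpatient setting. Placement is needed because phone type and setting do not capture distance.
2. Tabulate these by diagnosis. This shows whether the association exists.
3. Compare volume and amplitude between diagnoses within device and setting strata, or adjusted for them.
4. State how level is handled before classification, and rerun the classifier on level-normalised clips.
5. Report the AUC of a model using only device and setting beside the classifier's AUC, as a sensitivity analysis and not as a condition for any claim.

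The cost is a few recorded fields and some extra analyses, with no change to recruitment, care or sample size. Apparent accuracy may fall. Normalisation may remove true differences in loudness, and adjustment for setting may remove true information on severity, so adjusted and unadjusted results should be shown together. Usual placement is only a rough guide to distance, so some variation will remain.
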